3 STUDY DESIGN

[figure not shown]
3.1 General Study Design

This multicenter Phase 3 study is comprised of two parts. The first part of the study is a randomized, double blind, placebo-controlled, phase which aims to demonstrate efficacy and safety of BoNT/A-DP compared with placebo. The second part is an open label extension phase to evaluate efficacy after repeat treatments and long term safety.

Subjects can receive a maximum of four treatment cycles over the duration of the study, a single treatment in the first cycle compared with placebo, and up to three subsequent treatments in the open label extension study.

Subjects between 18 and 75 years of age, inclusive with moderate to severe glabellar frown lines at maximum frown with an important psychological impact as indicated by scores >0 on either the Emotional or Social Functioning subscales of the modified Skindex-16 (GL-QoL) will be enrolled in this study. Approximately 7 sites (United States (US) and Europe) will enroll in total 353 evaluable subjects with a variety of Fitzpatrick skin types. Applying a 15% drop out rate will result in a total number of completing subjects of about 300.

[figure not shown]
The overall study scheme is presented below:

[figure not shown]
The duration of study participation for each subject will be up to 14 calendar days of screening followed by 48 to 60 weeks of treatment (re-screening will not be permitted). The first treatment cycle will be a double blinded cycle followed by up to three open label treatment cycles. Each cycle will be at least 12 weeks and can be prolonged in 4-week increments, depending on treatment effect. Re-treatment is possible until study-week 48.

	Statistical Analysis Plan (SAP)	 <small>est. 1976</small>
--	--	---

Visit Scheme/Treatment Cycle 1 (double blind)

Visit Scheme/Treatment Cycles 2, 3, 4 (open label)

Statistical Analysis Plan (SAP)

CROMA
est. 1976

3.2 Randomization and Blinding

3.2.1 Randomization

This is a randomized, double blind, placebo-controlled efficacy and safety clinical study followed by an open label extension. Subjects will be randomly assigned to receive either BoNT/A-DP or placebo at a ratio of 3:1 respectively in the first treatment cycle. The 3:1 ratio in favor of active treatment versus placebo has been selected to increase the safety database size.

Randomization will be performed per study site via interactive web response system (IWRS). One unique randomization code will be assigned to each subject.

3.2.2 Blinding

For the first placebo controlled treatment cycle (the double blind cycle of this trial), BoNT/A-DP and placebo will be provided to the sites in glass vials. Since BoNT/A-DP-vials contain a pellet of lyophilized BoNT/A-DP, they can be discerned from placebo-vials (empty vials). However, after reconstitution by an unblinded study team member at the site, both will look identical (clear solution, comparable volume), thus maintaining the blind. The unblinded study team member preparing the Investigational Medicinal Product (IMP) at the study site must not, by any means, be involved in any other study data collection activities including adverse event (AE) assessment, case report form (CRF) completion, diary collection etc. IMP will be assigned to the subjects by IWRS with the lot number and kit number assigned corresponding to the group to which the subjects are assigned (blinded medication number and batch/lot number during the double blind phase of the study at the given site). The assigned vial will be reconstituted and will be forwarded to the investigator for injection. Specific Blinding Plans will be created at each study site during the Study Initiation visits.

3.2.3 Unblinding

The decision to unblind lies fully with the investigator. The randomization assignment should not be revealed before the study has been completed and the database has been cleaned and closed. The study will be unblinded using the Study Specific Unblinding Procedure (an unblinding module is standard on all blinded studies; also it is possible to grant access to regulatory unblinding users so that they can monitor the safety of the study, if required).

In case of emergency, the IMP administered to the subjects can be revealed using the unblinding function of the IWRS.

	Statistical Analysis Plan (SAP)	 <small>est. 1976</small>
--	--	---

In rare emergencies, unblinding may be necessary for the clinical management of an AE. Investigators should consider unblinding only if knowledge of the administered product will have an influence on the further treatment of the AE. In such events, the investigator should make every attempt to inform the Sponsor before breaking the blind or as soon as possible after unblinding has been performed. The [REDACTED] or CROMA medical team is available to discuss any unblinding need. However, such discussion is not mandatory. The investigator can always unblind as per his/her discretion if the actual treatment information is considered relevant for subsequent event treatment. Once unblinding has occurred, the site should immediately contact the [REDACTED] or CROMA medical team. Communication of the unblinding result is considered acceptable. It is at the discretion of the investigator to continue an unblinded subject in the study. The date and time of breaking the code, the reason for breaking the code, study product administered, subject identification number and randomization code will be documented within the IWRS. Subjects for whom the blind had been broken may continue in the study as per discretion of the Investigator.

3.3 Study Treatments and Assessments

Subjects will participate in this study for a duration of 50 to 62 weeks from signing the informed consent form (ICF) to the End of Study visit (i.e., up to 14 calendar days for screening, followed by 48 to 60 weeks study participation).

Subjects will receive a maximum of four permitted rounds of treatment, with a minimum interval between treatments of 12 weeks.

The first treatment cycle of the study will comprise of two treatment groups as follows:

- Group A (active): BoNT/A-DP (20 units, 0.5 mL).
- Group B (placebo control): sterile, 0.9% sodium chloride (0.5 mL).

An interim analysis (IA) will be performed when all subjects complete the re-evaluation for retreatment visit at week 16 of the first treatment cycle or complete the double blind phase (whichever occurs earlier). Refer to Section 8.9 for more details regarding the IA.

Eligible subjects will be randomized at baseline (day 0) to Group A or B to receive the first treatment in a 3:1 randomization scheme, respectively. Investigators and subjects will be blinded to the treatment administered and will evaluate the severity of glabellar lines independently. The subjects must perform their assessment independently and ideally before the investigator, to ensure they are not biased by the investigator. The same investigator must assess the subject at baseline and at the visits at weeks 1, 2 and 4 in the first treatment cycle.

After a screening period of up to 14 calendar days, subjects will receive the first treatment (BoNT/A-DP or placebo) and attend for visits at 1, 2 and 4 weeks after treatment and at 4-

Statistical Analysis Plan (SAP)

CROMA
est. 1976

weekly intervals thereafter for evaluation of efficacy and safety (primary and key secondary efficacy endpoints will only be evaluated in the first treatment cycle in comparison with placebo). Re-screening will not be permitted.

The effect of botulinum toxin typically lasts a few months, hence the first treatment cycle will last at least 12 weeks and will end when the subjects qualify for re-treatment.

Open Label Extension

After the first treatment cycle is completed, all subjects may enter the open label extension phase and will be dosed with BoNT/A-DP (20 U) for subsequent re-treatments.

Subjects will attend for visits at one and four weeks after re-treatment and at 4-weekly intervals thereafter. Additional telephone call follow-ups will take place in the open label extension phase two and eight weeks after each re-treatment. Each re-treatment cycle will last at least 12 weeks and will end when the subject qualifies for re-treatment or with the End of Study visit. According to the study schedule, a maximum of four treatments per subject (four treatment cycles) is permitted during the study time frame, with treatments separated by a minimum of 12 weeks.

A subject may move to the next treatment cycle if more than 12 weeks have passed since the previous treatment. Starting at week 12 and at 4-weekly intervals thereafter, subjects will attend the site for the Evaluation for Re-treatment visit. If the subject has a Facial Wrinkle Scale (FWS) score (at maximum frown) of ≥ 2 , as determined by both the subject using the Glabellar Line Scale for Subjects (GLS-S) and the investigator using the Glabellar Line Scale for Investigators (GLS-I), this visit on the same day at the same site visit will then be considered the End of Cycle visit and all other criteria required to determine eligibility for re-injection will be assessed e.g. negative urine pregnancy test (in women of child-bearing potential), lack of infection or inflammation in the planned injection area etc. Furthermore, all additional tests e.g. laboratory tests required for final cycle assessment will be performed. If the subject qualifies for re-treatment, on the same day at the same site visit, the subject will then enter the next treatment cycle and will receive the next study drug treatment as part of the Re-Treatment visit (i.e., day 0 of the next treatment cycle).

If the FWS score (at maximum frown) is assessed as ≥ 2 by both the investigator and the subject, but the additional criteria for reinjection are not met, e.g. relevant infection or inflammation at the injection site, the subject may attend for a visit 4 weeks thereafter. Subjects with a positive pregnancy test, or subjects who do not agree to re-treatment, will be

	Statistical Analysis Plan (SAP)	 <small>est. 1976</small>
--	--	---

withdrawn from the study and the End of Study visit will be conducted at the earliest opportunity.

If at an Evaluation for Re-treatment visit the subject wants to get re-treated, but the investigator does not agree or vice versa (i.e., the FWS score is not \geq at least 2 by both assessments), the subject will return to the site four weeks thereafter for another Evaluation for Re-treatment visit. There is no limit to the number of Evaluation for Re-treatment visits. In order to consider a visit as the End of Cycle visit, there must always be agreement between investigator and subject on a FWS score (at maximum frown) of ≥ 2 .

End of Study Visit

The End of Study visit can take place in four-weekly intervals from study-week 48 until study-week 60. The last study drug re-treatment will be administered no later than week 48. For subjects receiving a re-treatment at week 48, the last cycle will end 12 weeks later at week 60 (i.e., End of Study visit).

The End of Study visit will take place at week 48 if the week 48 visit is an Evaluation for Re-treatment visit and the subject does not meet the criteria for re-treatment in case this visit is 12 or more weeks after the last treatment. As week 48 is the last possible time point for re-treatment, such subjects will continue with all additional assessments of the End of Study visit on the same day. For subjects having received their last injection eight weeks or less prior to week 48, the End of Study visit will take place 12 weeks after the last study drug treatment was given, e.g. week 52 if the subject was re-treated at week 40.

For subjects who are prematurely discontinued from the study (at any time), the End of Study visit will take place within one week of discontinuation.

A detailed description of procedures and assessments to be conducted during this study is summarized in the Scheduled of Study Assessments in Table 1 below.

COVID-19 Pandemic

Due to the COVID-19 pandemic, which touched the world mainly the first 6 months of 2020, it has been allowed that visits were done remotely instead of physically when site was closed.

All re-treatments were put on hold between the 16th March and 5th May 2020 due to concerns that the subject will not be able to return for Week 1 and Week 4 assessments. Consequently, when a subject was eligible for re-treatment at a visit, the injection has been delayed until the subject could go back to site (if the injection is done before or at Week 48).

	Statistical Analysis Plan (SAP)	croma est. 1976
---	--	---------------------------

Subjects have been classified as study completer if the subject was eligible for re-treatment before or at Week 48 but never re-treated due to pandemic hold. More instructions can be found in the CRF completion guidelines document.

Statistical Analysis Plan (SAP)

[figure not shown]

Table 1: Schedule of Study Assessments

Statistical Analysis Plan (SAP)

croma
est. 1976

TC = telephone contact: including assessment of concomitant medication, AEs and AESIs¹⁵ (as per AESI manual) on weeks 2 and 8 of each open label cycle (visits 9, 11, 14, 16, 19 and 21). If an AESI is reported during a telephone contact, subjects will be asked to come to the site for further assessment including a targeted physical examination as soon as possible) * Visit numbers correspond with specific treatment and assessments. If subjects are not eligible for re-treatment at the "Evaluation for Re-treatment" visit, they will return at 4 weekly intervals thereafter, until they are eligible for treatment. The subsequent visit number for the cycle will remain the same, but will be amended with "a, b, c" etc., corresponding to the time extended (at 4 weekly intervals) in that treatment cycle. For example, the first evaluation for re-treatment is at visit 7, week 12, however for subjects who are not eligible at week 12, but at week 16, this visit will be denoted "visit 7a", while "visit 7b" will denote week 20 in the first cycle and "visit 7c" will denote week 24 etc., with each additional letter corresponding to a time point 4 weeks later in that cycle.

** Time differences are measured from the previous treatment administered. A time deviation of \pm 5 days is allowed for each visit, except for the week 1 and week 4 visit in each treatment cycle where a time deviation of \pm 2 days is permitted. Sites must adhere to the schedule of events and visit windows and subjects must ensure they are available for those visits. However, if for practical reasons e.g. public holidays, a visit window cannot be met, a visit can be scheduled as close as possible to that visit window. Any deviation from the visit schedule and its associated time windows will still be documented as a protocol deviation.

*** Full physical examination will include neurological assessment (including extraocular movements and cranial nerves) as well as assessment for muscle weakness. In addition, if the subject reports any symptoms related to Adverse Events of Special Interest (as detailed in the AESI Manual) a focused physical examination, to evaluate these symptoms will also be undertaken.

§ The ECG performed at screening is the baseline ECG. Laboratory and Anti-drug-antibody (ADA) test samples from screening are considered baseline values.

1 Depending on the duration of treatment effect, a maximum of 4 treatments is permitted.

2 Evaluation for re-treatment takes place at the earliest at 12 weeks after the first/previous treatment. Subjects who do not qualify for re-treatment at week 12 will have the option (pending eligibility) for re-treatment at 4-weekly intervals thereafter, until they are eligible for re-treatment. Once the subject is eligible for re-treatment, the end of cycle procedures will take place and the subject can receive re-treatment (i.e. the end of cycle visit and the re-treatment visit will be conducted on the same day as the Evaluation for Re-treatment visit).

3 The latest time for re-treatment is study week 48; if a subject is not eligible for re-treatment at study week 48, the End of Study visit will be completed.

4 The End of Study visit can take place in four-weekly intervals from study-week 48 until study-week 60. For subjects receiving re-treatment at week 48, the last cycle will end 12 weeks later at week 60 (=End of Study visit). End of Study visit will take place at week 48 if week 48 visit is an Evaluation for Re-treatment visit and the subject is not meeting the criteria for re-treatment. For subjects having received their last injection 8 weeks or less prior to week 48, the End of Study visit will take place 12 weeks after the last study drug treatment was given, e.g. week 52 if subject was retreated at week 40. For subjects that get prematurely discontinued from the study (at any time) the End of Study visit will take place within 1 week of discontinuation.

5 Only in women of child-bearing potential; blood serum test at screening and End of Study visit; otherwise urine dip stick.

6 Vital signs include blood pressure (diastolic /systolic) and pulse.

7 Laboratory Assessments: Hematology and Serum Chemistry, details in Section 11.15 of the study protocol..

Statistical Analysis Plan (SAP)

croma
est. 1976

- 8 Investigator's assessment of glabellar line severity at maximum frown and at rest. Assessment will be made using the 4-point FWS [GLS-I] (0=none, 1=mild, 2=moderate, 3=severe) and will be recorded in the CRF.
- 9 Subject's assessment of glabellar line severity at maximum frown and at rest. Assessment will be made using the 4-point FWS [GLS-S] (0=none, 1=mild, 2=moderate, 3=severe). Subject Assessment will be performed before (ideally) and always independently of investigator assessment and will be recorded in the CRF)
- 10 Photographs of subject's glabellar lines (at maximum frown and at rest) will be taken at C1 Randomization, C1 week 2, C1 week 4 and each C1 Evaluation for Re-Treatment visit in Cycle 1 until the subject qualifies for re-treatment in order to provide evidence of effect and confirm that the subject did not qualify for re-treatment on the preceding evaluation for re-treatment visit. Although a photograph will be taken at each Evaluation for Re-treatment visit, only the photo of the visit preceding the re-treatment visit will be reviewed by the independent reviewers.
- 11 Modified Skindex-16 (GL-QoL) and FACE-Q Appraisal of Lines Between Eyebrows and Age Appraisal VAS scales will be used to measure psychological impact and concerns relating to their glabellar lines, respectively (and will be recorded in the CRF).
- 12 Treatment satisfaction will be determined using the FACE-Q Satisfaction with Outcome Scale (will be recorded in the CRF).
- 13 Subjects will be monitored for AEs during 30 minutes after administration of the IMP. No additional questioning of AESIs directly post-injection.
- 14 Anti-drug-antibody (ADA) test. If positive, serum samples will be tested for the presence of neutralizing antibodies.
- 15 General, non-leading AE questioning as well as active AESI questioning at each indicated visit. The first AESI questioning will be completed at Baseline visit in order to obtain a full baseline status of any concomitant diseases prior to the first IMP injection.
AESI Questioning: active questioning by guided review of systems (ROS) as per AESI manual. If an AESI is reported, a targeted physical examination around the area of the reported AESI must follow.

AE: Adverse event; AESI: Adverse event of special interest; C: Cycle; CRF: Case report form; D: Distribution of subject diary; ECG: Electrocardiogram; FWS: Facial Wrinkle Scale; GL-QoL: Glabellar Line Quality of Life Scale; IMP: Investigational medicinal product; R:Return of subject diary; TC: telephone call; VAS: Visual analog scale.

Statistical Analysis Plan (SAP)

CROMA
est. 1976

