7.3 Eligibility Criteria for Re-treatment

The following criteria **MUST** be met for re-treatment:

- At time of re-treatment subject does not have relevant changes to their health status from enrollment, which would have prevented subject's entry into the study according to the inclusion and exclusion criteria.
- The subject must have been randomized to receive treatment and must have received at least one treatment (BoNT/A-DP or placebo).
- A minimum of 12 weeks must have elapsed since the previous study treatment.
- The subject's glabellar lines at maximum frown must have relapsed to a FWS score of 2 or 3 as determined by both the investigator and the subject.
- No relevant infection or inflammation in the planned injection area.
- Negative urine pregnancy test, in women of child-bearing potential.
- The subject must have received fewer than four study treatments.
- The subject must agree and consent to re-treatment.
- Re-treatment will be performed at the latest by week 48.

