10.1.2 Photo-evaluator Assessment

Photography will be performed by specifically trained personnel in accordance with the relevant imaging manual. Photographs of subjects at maximum frown and at rest will be taken in the first treatment cycle at the following visits: baseline before the first treatment, study visits 2 and 4 weeks after the first treatment and at the Evaluation for Re-treatment visits, i.e. week 12 after baseline and 4 weekly thereafter until the subject qualifies for re-treatment. Selected photographs will subsequently be assessed by independent blinded raters. Although a photograph will be taken at each evaluation for the re-treatment visit, only the photograph of the visit preceding the re-treatment visit will be reviewed by the independent raters (in addition to the photographs at baseline, week 2 and week 4) and the data will be included in the analysis of additional secondary efficacy endpoints.

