4.3 Additional Secondary Efficacy Endpoints

The additional secondary efficacy endpoints of this study are:

2. The percentage of responders at maximum frown (as defined in 4.1 above) at week 12 (after the first treatment with BoNT/A-DP or placebo).
3. The percentage of responders at week 16 (after the first treatment).
4. The percentage of responders at week 20 or later (after the first treatment).
5. The proportion of subjects with a ≥ 1 point reduction in FWS score at rest at week 4 in the first treatment cycle, based separately on the investigators' and the subjects' in-clinic assessments (applicable only for subjects who have a FWS score at rest ≥ 1 at baseline).
6. The proportion of responders among BoNT/A-DP and placebo groups with a FWS score at maximum frown of 0 or 1 and an improvement of ≥ 2 points in FWS score (at maximum frown) during the first treatment cycle visit relative to baseline, based on both the investigators' and the subjects' in-clinic assessments (composite endpoint, at weeks 1, 2 and 8).
7. The proportion of subjects with ≥ 2 point and ≥ 1 point reduction in FWS score (at maximum frown) in the BoNT/A-DP and placebo groups during the first treatment cycle

Statistical Analysis Plan (SAP)

CROMA
est. 1976

visit relative to baseline, based on the independent rater's assessment of photographs (at baseline and visits 2, 4, 12, 16 and 20 weeks after treatment, within the first treatment cycle).

8. Time to onset of effect in the BoNT/A-DP and placebo groups in the first treatment cycle, as measured at weeks 1, 2 and 4 based separately on subject and investigator assessments. Onset of effect defined as at least a 1 point improvement in FWS score from baseline (at maximum frown). In addition, onset of effect will be assessed by subjects daily in the first 2 weeks after treatment, by recordings in the subject diary.
9. The extent of subject perceptions of effect of, and satisfaction with, treatment, in the BoNT/A-DP and placebo groups, during each treatment cycle, as assessed by the FACE-Q Satisfaction with Outcome Scale.
10. The proportion of subjects with a ≥ 1 point reduction in FWS score at rest in the BoNT/A-DP and placebo groups, relative to baseline, during the first treatment cycle, based on the independent rater's assessment of photographs.

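### Independent-rater responder proportions by arm at weeks 12, 16 and 20 (endpoint 7) cannot be estimated when raters read only one late photograph per subject

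*SAP*

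**What the plan says.** Endpoint 7 (protocol 6.4.2.2, SAP 4.3, repeated in SAP section 9) is the proportion of subjects in each arm with a reduction of at least 2 points, and of at least 1 point, in FWS at maximum frown, scored by independent raters from photographs "at baseline and visits 2, 4, 12, 16 and 20 weeks after treatment, within the first treatment cycle". SAP 8.6.4 gives these proportions a site-stratified CMH test and a Pearson chi-square test, or Fisher's exact test when counts are small.

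The reading rule is narrower. Protocol 10.1.2 schedules cycle-1 photographs at baseline, at "study visits 2 and 4 weeks after the first treatment and at the Evaluation for Re-treatment visits"; week 8 is not among them. It then states that "only the photograph of the visit preceding the re-treatment visit will be reviewed by the independent raters", besides those from baseline, week 2 and week 4, and that the readings feed the additional secondary efficacy analyses. Footnote 10 of SAP Table 1 repeats the restriction ("only the photo of the visit preceding the re-treatment visit will be reviewed by the independent reviewers") and gives its purpose: to show effect and to confirm that the subject was not yet eligible at the evaluation visit before re-treatment.

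Two further rules fix who is read when. Re-treatment happens on the day of qualification: "the end of cycle visit and the re-treatment visit will be conducted on the same day as the Evaluation for Re-treatment visit" (SAP Table 1, footnote 2). To qualify, the subject's lines "must have relapsed to a FWS score of 2 or 3 as determined by both the investigator and the subject" (protocol 7.3), at week 12 at the earliest.

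**The concern.** An endpoint at three late weeks needs a reading for every subject at each of those weeks, or a rule for those without one. The reading rule supplies one late reading per subject at most. Which week it falls in, and whether it exists, is decided by events after randomisation that treatment strongly affects. A test comparing the arms on such readings no longer compares randomised groups.

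At stake is the only rating of late response made outside the clinic. If the late rows of endpoint 7 were reported as planned, a reader could take them as response rates for the two randomised arms, which they would not be.

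**Working it through.** **Step 1: which photographs are read.** Evaluation visits are at week 12 and every 4 weeks after, and re-treatment is on the day of qualification, so the preceding visit is normally 4 weeks earlier.

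| Re-treated at | Late photograph read |
|---|---|
| Week 12 | none (preceding visit is week 8, no photograph) |
| Week 16 | week 12 only |
| Week 20 | week 16 only |
| Week 24 | week 20 only |
| Never in cycle 1 | none defined |

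The sets read at weeks 12, 16 and 20 do not overlap. Membership mostly means that at least one clinic assessor scored FWS below 2 at that visit, because both must score 2 or 3 for re-treatment. A few subjects enter for other reasons: another re-treatment criterion not met (protocol 6.3.2), or the COVID-19 hold (SAP 3.3). The week-12 set also leaves out the longest responders, who are re-treated at week 20 or later. This step uses the documents' rules only.

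**Step 2: is there a rule for the unread?** SAP 7.2.1 covers in-clinic FWS and the questionnaire scores. SAP section 9 adds worst-case and median handling for the rater endpoints but does not widen what is read. Neither gives a denominator for unread photographs.

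**Step 3: size, as an illustration.** The plan states no number of late readings. Its accrual figure reproduces: 353 × 0.85 = 300.05, about 300. Arms at 3:1 are 353 × 3/4 = 264.75 active and 353 × 1/4 = 88.25 placebo.

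Assumed proxy for not yet eligible: the composite rate of at least 1-point improvement at weeks 12, 16 and 20 (protocol 4.4.2.1 and 4.4.2.2).
- BLESS I: active 45.1%, 20.8%, 9.9%; placebo 1.2%, 0.6%, 0.0%.
- BLESS II: active 40.5%, 12.1%, 4.7%; placebo 2.1%, 0.0%, 0.0%.

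Readings at week t = arm size × (rate at t − rate at t+4). For week 20 the whole week-20 rate is used as an upper limit.

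| | Active, BLESS I | Active, BLESS II | Placebo, BLESS I / II |
|---|---|---|---|
| Week 12 | 264.75 × 0.243 = 64 | 264.75 × 0.284 = 75 | 0.5 / 1.9 |
| Week 16 | 264.75 × 0.109 = 29 | 264.75 × 0.074 = 20 | 0.5 / 0 |
| Week 20 (at most) | 264.75 × 0.099 = 26 | 264.75 × 0.047 = 12 | 0 / 0 |

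Active subjects re-treated at week 12, with no late reading: 264.75 × 0.549 = 145 (BLESS I) or 264.75 × 0.595 = 158 (BLESS II).

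**Step 4: a wider placebo bound.** Both baseline scores are 2 or 3, so failing the FWS criterion requires at least a 1-point improvement by at least one assessor. From the week-4 placebo rates, investigator + subject − both:
- BLESS I: 9.7 + 7.4 − 1.7 = 15.4%, and 88.25 × 0.154 = 13.6.
- BLESS II: 3.8 + 9.4 − 1.9 = 11.3%, and 88.25 × 0.113 = 10.0.

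If later placebo rates are no higher than at week 4, at most about 10–14 placebo subjects contribute one late reading each, over all late visits together. Across about 7 sites (SAP 3.1) that is about 2 per site at most, too few for a site-stratified test at three separate weeks.

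**Step 5: direction of bias at week 12.** If only read photographs form the denominator, the active set is largely selected for persisting effect. If the denominator is the FAS and unread counts as non-response, the active proportion cannot exceed 64/265 = 24% or 75/265 = 28%, against clinic proxies of 45.1% and 40.5%. The two conventions push in opposite directions.

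**The case against.** The selective reading is deliberate. Footnote 10 presents the late photograph as a check that the subject was not eligible at the preceding visit, and one photograph is enough for that. The endpoint is exploratory under SAP 8.6.1.1. Secondary objective 3 ties duration of effect to investigator and subject assessments, and the in-clinic responder endpoints at weeks 12, 16 and 20 have explicit missing-data and re-treatment rules. All of this stands, and it limits the consequence. It does not align endpoint 7 with the reading rule, since protocol 10.1.2 sends the same readings into the efficacy analysis.

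The counts are also open to challenge. A change from 3 to 2 counts as improvement yet meets the re-treatment criterion. A score of 0 or 1 from one assessor blocks re-treatment without composite improvement. Subtracting rates between visits assumes a common denominator that the protocol does not state. The proxy can err either way, so the counts are illustrative only. The mismatch does not depend on them.

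The preceding visit could be read as the evaluation visit of the same day. Each subject would still have one late reading, now selected for relapse, and arm-level proportions would still be missing. Footnote 10's stated purpose favours the reading used here.

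A reader might infer that the rater results would overstate the duration of effect. The documents do not support that: the direction turns on a denominator the SAP leaves undefined.

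**Conclusion.** The listed late weeks of endpoint 7 and the photograph-reading rule cannot both be carried out as written. Proportions for the randomised arms at weeks 12, 16 and 20 cannot be estimated. A proportion among those read can be computed, but it is not the stated endpoint, and any such figure is biased in a direction the SAP leaves undetermined. On the assumed proxy, roughly a quarter of the active arm would be read at week 12, about a tenth at week 16, and almost no placebo subjects at any late visit. The wider placebo total of about 10–14 assumes rates no higher than at week 4 and excludes deferrals for non-FWS reasons.

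The scope is limited. Rater results at weeks 2 and 4, the primary and key secondary tests, and the in-clinic duration endpoints are not affected. Endpoint 10 (at rest) draws on the same photographs but lists no weeks, so it needs clarifying, not correcting. The point should be settled before the rater data are analysed.

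**What to change.** Choose one of two changes, and make protocol 10.1.2, footnote 10 of SAP Table 1, endpoint 7 and SAP 8.6.4 agree with it.

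(a) Have the existing raters read all cycle-1 evaluation photographs already taken. Week 12 can then be analysed on the randomised arms, with up to about 265 active and 88 placebo readings (about 225 and 75 after 15% dropout). For weeks 16 and 20, apply the SAP's in-clinic rule that a subject re-treated before the visit is a non-responder, and state how a missing photograph counts. That rule brings the clinic's re-treatment decision into the rater endpoint, so weeks 16 and 20 would no longer be fully independent of the clinic; the SAP should say so. Cost: more readings, with no new visits or photographs.

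(b) Remove weeks 12, 16 and 20 from endpoint 7, state that endpoint 10 is analysed at weeks 2 and 4 only, and report the single late photograph descriptively as verification of non-eligibility. Cost: wording, and the loss of the late rater time points.
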